4. STUDY POPULATION

4.1. Participant Inclusion Criteria

To be eligible to participate in this study, an individual must meet all of the following criteria:

1. Written informed consent and HIPAA authorization for release of personal health information. NOTE: HIPAA authorization may be included in the informed consent or obtained separately
2. Qualify for anti-PD-1 therapy based on current guidelines at the time of registration. This includes the standard requirement for the participant's tumor to have been previously determined to express PD-L1 with a combined positive score ≥ 1 , as determined by an FDA-approved test.
3. Age 18 years and older at the time of consent
4. ECOG Performance Status of 0-2 within 30 days prior to enrollment
5. Histologically proven diagnosis of head and neck squamous cell carcinoma that is metastatic or recurrent disease that is surgically incurable
6. Prior cancer treatment other than anti-PD-1 therapy must be completed at least 30 days prior to registration and the subject must have recovered from all reversible acute toxic effects of the regimen (other than alopecia) to \leq Grade 1 or baseline. Patients may not undergo concurrent anti-cancer treatment during treatment with protocol therapies. This includes no treatment with growth factors, tyrosine kinase inhibitors, tumor-specific antibodies, or cytotoxic chemotherapies such as cisplatin. Patients who have previously or are currently taking an anti-PD-1 therapy are eligible for this study if they meet eligibility criteria 2. Patients who have previously taken any other immune checkpoint inhibitor are eligible as long as they have completed that treatment at least 30 days prior to registration and meet all other eligibility criteria.
7. Subjects with central nervous system (CNS) metastases are eligible if the CNS lesions are stable for at least 2 months and if tapered off treatment doses of systemic corticosteroids for at least 2 weeks prior to enrollment on the trial. Management with maintenance physiologic doses of corticosteroids (equivalent doses of prednisone ≤ 10 mg daily) is acceptable.
8. Subjects must have an "index" tumor that: 1) is deemed by the treating radiation oncologist to potentially benefit from palliative radiation 2) is amenable to biopsy, 3) is ≥ 1 cm in longest dimension.
9. Demonstrate adequate organ function as defined in the table below; all screening labs to be obtained within 30 days prior to enrollment

System	Laboratory Value
Hematological	

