5.8.1. Selection of an Index Tumor Site

From the tumor site(s) receiving palliative RT, a targeted (index) tumor will be selected at the discretion of the attending physician based on need for palliative radiation, ease of being able to obtain post-treatment biopsies from that site, and size at least 1 cm in longest dimension. Whenever possible, the targeted region should not have received RT prior to enrollment in this study. Palliative RT may be delivered to other sites of disease if deemed necessary and safe.

5.8.2. *Radiation Dose (SOC)*

The treating physician will use his/her discretion to decide between a dose and fractionation schedule of 8 Gy x 3 or 4 Gy x 5. Radiation can be delivered either daily or every other day and is generally provided on weekdays only. The treating physician will also use his/her discretion if multiple sites of disease will be treated with RT. If multiple sites of disease are being treated, these treatments should conclude between days -7 to -3 relative to the second doses of anti-PD-1 and NKTR-214.

5.8.3. *Radiotherapy Delivery (SOC)*

RT delivery will follow standard practice for palliative RT treatment and will utilize megavoltage (MV) photons or electrons. Any number or arrangement of beams may be used at the discretion of the treating physician to achieve target coverage and conformality.

Treatment Simulation, Subject Positioning and Set-up

Subject will be positioned in a comfortable position. Any immobilization apparatus may be used at the discretion of the treating physician as long as it does not interfere with the proper functioning of any necessary treatment planning or image-guidance systems. A CT simulation will be performed for all patients to facilitate treatment planning, consistent with standard practice approaches for the planning of palliative RT. The planning CT scan may be done with intravenous contrast if this is beneficial for target or normal tissue segmentation. CT scan thickness will be ≤ 0.3 cm. Planning CT scan will be acquired with the subject in the same position and using the same immobilization device as for treatment. At a minimum, all tissues within 5 cm of the target volume will be included in the CT scan. For spinal lesions treated with 8 Gy x 3, a pre-treatment MRI is required to assess the extent of disease and position of the cord. This must be fused with the planning CT scan.

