11.2. Sample Size Considerations

This study will enroll 24 participants to test the hypothesis that the combination of NKTR-214 with palliative radiation and anti-PD-1 therapy results in an ORR $\geq 44\%$. Under the null hypothesis for ORR ≤ 0.22 , based on one-sided one sample proportion test with type I error of 0.1, the expected power levels to detect alternative ORRs of 0.35, 0.4, and 0.45 are 55 %, 74 %, 87 % respectively. The null hypothesis will be rejected and superiority concluded if 8 or more responses are observed in 24 participants. This design yields a type I error rate of .04 and power of .8 when the true response rate is 44 %.

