11.3.1. Analysis Plans for Primary Objective

ORR will include confirmed complete response (CR) + confirmed partial response (PR) and will be assessed based on RECIST 1.1 criteria. ORR will be reported with the 95 % confidence interval (CI). Progression of any radiated tumors will be considered in this evaluation but response of radiated tumor(s) will not be considered as evidence of response for the purpose of this study unless all tumor sites are radiated.

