11.3.4. Subgroup Analyses

Subgroup analyses for ORR will be performed on the basis of high versus low tumor mutation burden, high versus low PD-L1 expression on cycle 1 index tumor biopsy, HPV/EBV status, metastatic versus locally recurrent disease, and tobacco smoking history.

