12. CRITERIA FOR DISEASE EVALUATION

The following sections describe the recommended method to track disease response per the RECIST1.1 (see Eisenhauer EA et al. *New response evaluation criteria in solid tumors: revised RECIST guideline (version 1.1)*. Eur J Can, 2009.45:p.228-247). Progression of any radiated tumors will be considered in this evaluation but response of radiated tumor(s) will not be considered as evidence of response for the purpose of this study.

Refer to the RECIST1.1 publication for complete details on these criteria.

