12.3. Target Lesions

All measurable lesions up to a maximum of 2 lesions per organ and 5 lesions in total, representative of all involved organs, should be identified as target lesions and recorded and measured at baseline. Target lesions should be selected on the basis of their size (lesions with the longest diameter), be representative of all involved organs, but in addition should be those that lend themselves to reproducible repeated measurements. It may be the case that, on occasion, the largest lesion does not lend itself to reproducible measurement in which circumstance the next largest lesion that can be measured reproducibly should be selected. A sum of the diameters (longest for non-nodal lesions, short axis for nodal lesions) for all target lesions will be calculated and reported as the baseline sum diameters. If lymph nodes are to be included in the sum, then only the short axis is added into the sum. The baseline sum diameters will be used as reference to further characterize any objective tumor regression in the

measurable dimension of the disease. Target lesions will not include radiated tumor sites for this study unless all tumor sites have been radiated.

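### The ORR comparison of metastatic with locally recurrent disease is confounded with the rule for scoring participants whose tumor sites were all irradiated

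*Combined protocol and SAP*

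**What the plan says.** Section 11.3.4 plans ORR subgroup analyses on five factors, among them "metastatic versus locally recurrent disease, and tobacco smoking history". It names no test, model, adjustment or decision rule.

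Section 4.1 admits "metastatic or recurrent disease that is surgically incurable" and requires an index tumor that "is deemed by the treating radiation oncologist to potentially benefit from palliative radiation". Section 5.8.1 picks the index tumor from the sites receiving radiation and adds: "Palliative RT may be delivered to other sites of disease if deemed necessary and safe". Under 5.8.3, a participant who decides against radiation before any fraction is given leaves the study. The number of sites treated is left to the physician (5.8, 5.8.2).

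The response rule appears in two forms:

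- With an exception. Section 11.3.1: "response of radiated tumor(s) will not be considered as evidence of response for the purpose of this study unless all tumor sites are radiated". Section 12.3: "Target lesions will not include radiated tumor sites for this study unless all tumor sites have been radiated".
- Without one. Section 12: "response of radiated tumor(s) will not be considered as evidence of response for the purpose of this study". The primary endpoint table in 2.1 says the same.

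**The concern.** Anyone who stays on study with a single disease site has all sites irradiated, and that is the condition on which the response rule turns. Disease confined to a local recurrence is more likely to lie wholly within the radiation field. Metastatic disease is more likely to leave lesions outside it. The subgroup label is therefore likely to be associated with how response is scored.

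If the exception applies, locally recurrent participants are more often scored on lesions that radiation alone may shrink, and their ORR tends to look better. If it does not apply, they are more often unable to show a response, and their ORR looks worse. Choosing one rule settles the direction but leaves the confounding in place. At stake is the reading of a prespecified analysis: an apparent difference by disease extent could come from the scoring.

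**Working it through.** The plan states no figure for this subgroup, so there is none to reproduce. The 8-of-24 rule in 11.2 concerns the whole cohort and is not used here.

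**Inputs from the documents.** 24 participants (11.2); null ORR 22% (1.2, 11.2); target ORR 44% (11.2).

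**Assumptions, because the documents give no values.** Subgroups of 12 and 12. *p* is the response probability on non-irradiated lesions, the same in both groups, at 0.22 or 0.44. *f* and *g* are the shares of locally recurrent and metastatic participants with all sites irradiated. *r* is the probability that an all-irradiated participant is scored a responder: 0 if in-field response never counts, or 0.4 to 0.7 if it does. All-irradiated participants stay in the denominator. The test is Fisher's exact test at two-sided 0.05, for illustration only.

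**Formulas.**

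- Locally recurrent ORR = (1 − f)p + f·r
- Metastatic ORR = (1 − g)p + g·r
- Gap = (f − g)(r − p)

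The gap is zero if f = g or if r = p. It is negative when in-field response never counts and positive when it counts and r exceeds p.

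**Example.** With p = 0.22, r = 0.7, f = 1 and g = 0, the gap is 1 × (0.7 − 0.22) = 0.48. With p = 0.44, r = 0 and the same shares, it is 1 × (0 − 0.44) = −0.44.

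**Results with g = 0.** Each cell gives the gap (locally recurrent minus metastatic, percentage points), then the rejection probability, from exact enumeration of two independent binomials.

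| Rule | p | r | f = 0.5 | f = 0.75 | f = 1 |
|---|---|---|---|---|---|
| In-field never counts | 0.22 | 0 | −11; 0.03 | −16.5; 0.05 | −22; 0.10 |
| In-field never counts | 0.44 | 0 | −22; 0.11 | −33; 0.28 | −44; 0.67 |
| In-field counts | 0.22 | 0.4 | +9; 0.03 | +13.5; 0.05 | +18; 0.08 |
| In-field counts | 0.22 | 0.7 | +24; 0.13 | +36; 0.31 | +48; 0.56 |
| In-field counts | 0.44 | 0.4 | −2; 0.02 | −3; 0.02 | −4; 0.02 |
| In-field counts | 0.44 | 0.7 | +13; 0.05 | +19.5; 0.09 | +26; 0.16 |

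With no artefact the rejection probability is 0.013 at p = 0.22 and 0.022 at p = 0.44.

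**Incomplete separation, f = 0.75 and g = 0.10.** The gap is 0.65(r − p).

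- Never counts: −14.3 points (rejection 0.04) at p = 0.22; −28.6 points (0.21) at p = 0.44.
- Counts, r = 0.4 to 0.7: +11.7 to +31.2 points (0.04 to 0.23) at p = 0.22; −2.6 to +16.9 points (0.02 to 0.07) at p = 0.44.

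**Equal shares.** With f = g the gap is zero under either rule. The artefact therefore comes from the difference in shares, and comparing within irradiation status removes it.

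**The case against.** The strongest reply is that the documents tie the scoring switch to irradiation of all sites, not to disease state. A reader might infer that locally recurrent participants are read on irradiated lesions and metastatic participants on non-irradiated ones. The text does not support that. A locally recurrent participant with one untreated measurable lesion is scored outside the field, and a metastatic participant with every site treated is not. The association is a tendency of unknown strength. This stands.

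The size is also open. The largest gaps need complete separation. At f = 0.25 and g = 0 the rejection probability is only 0.016 to 0.040 across the same values of p and r. This stands too, and is why the result is given as a range.

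Section 11.3.4 names no test, and nothing says this subgroup will choose a later trial's population. Both are correct, so the rejection rates are illustrative. The gap in ORR needs no test, however, and would appear in a descriptive table.

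Finally, the never-counts branch exists only because 2.1 and 12 omit the exception. It also assumes that all-irradiated participants stay in the denominator, and 11.3 describes evaluability in two different ways. Reconciling the text could remove that branch. It would leave the other, in which in-field response is compared partly with out-of-field response.

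**Conclusion.** The concern holds in limited form. As planned, the comparison is confounded with the scoring rule, and following the plan exactly can produce a difference where the regimen works equally well in both groups. The direction depends on which response rule governs.

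The size cannot be derived from the documents. With 12 v 12, f from 0.5 to 1, g = 0 and true ORR of 22% to 44%, the absolute gap runs from near 0 to about 48 points and the rejection probability from 0.02 to 0.67. With shares of 0.75 against 0.10 the rejection probability is about 0.02 to 0.23. These figures rest on the assumed shares, in-field response rates, subgroup sizes and test.

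A reader might take a gap of 44 to 48 points as the expected bias, or take the point as undermining the trial's main result. Neither follows. The first needs every locally recurrent participant, and no metastatic one, to have all sites irradiated. As to the second, this is one of five exploratory subgroup factors and the success rule uses overall ORR. Priority is low.

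**What to change.** In 11.3.4:

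1. Present ORR for metastatic and locally recurrent disease cross-tabulated by all-sites-irradiated status (yes or no), with n, responses and 95% CI in each cell. Define status by the radiation given before cycle 2, because 5.8.3 permits further courses after cycle 3.
2. Base any statement about differential efficacy by disease extent only on participants with at least one non-irradiated target lesion, scored on non-irradiated lesions.
3. State that the unstratified comparison is not evidence of differential efficacy.

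Separately, reconcile 2.1, 11.3.1, 12 and 12.3 so that one response rule applies throughout.

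The cost is wording and a slightly larger table, built from radiation and lesion records the study already keeps. Nobody is dropped from the tabulation. The drawback is small cells. With 12 locally recurrent participants, a share of 0.75 leaves 12 × 0.25 = 3 in the cell that supports inference, and a share of 1 leaves none. If that cell is empty or nearly so, report the comparison as not interpretable.

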12. CRITERIA FOR DISEASE EVALUATION

The following sections describe the recommended method to track disease response per the RECIST1.1 (see Eisenhauer EA et al. *New response evaluation criteria in solid tumors: revised RECIST guideline (version 1.1)*. Eur J Can, 2009.45:p.228-247). Progression of any radiated tumors will be considered in this evaluation but response of radiated tumor(s) will not be considered as evidence of response for the purpose of this study.

Refer to the RECIST1.1 publication for complete details on these criteria.

12.1. Measurable Disease

Measurable disease is defined as the presence of at least one measurable lesion. Measurable lesions are defined as those that can be accurately measured in at least one dimension (longest diameter to be recorded) as ≥ 20 mm by chest x-ray, as ≥ 10 mm with CT scan, or ≥ 10 mm using standard clinical measurements, such as calipers or single use measuring paper by clinical exam. All tumor measurements must be recorded in millimeters (or decimal fractions of centimeters).

12.1.1. Malignant Lymph Nodes

To be considered pathologically enlarged and measurable, a lymph node must be ≥ 15 mm in short axis when assessed by CT scan (CT scan slice thickness recommended to be no greater than 5 mm). At baseline and in follow-up, only the short axis will be measured and followed.

12.2. Non-measurable Lesions

All other lesions (or sites of disease), including small lesions (longest diameter < 10 mm or pathological lymph nodes with ≥ 10 to < 15 mm short axis), are considered non-measurable disease. Bone lesions, leptomeningeal disease, ascites, pleural/pericardial effusions, lymphangitis cutis/pulmonitis, inflammatory breast disease, and abdominal masses (not followed by CT or MRI), are considered as non-measurable.

NOTE: Cystic lesions that meet the criteria for radiographically defined simple cysts should not be considered as malignant lesions (neither measurable nor non-measurable) since they are, by definition, simple cysts. 'Cystic lesions' thought to represent cystic metastases can be considered as measurable lesions, if they meet the definition of measurability described above. However, if non-cystic lesions are present in the same subject, these are preferred for selection as target lesions.

12.3. Target Lesions

All measurable lesions up to a maximum of 2 lesions per organ and 5 lesions in total, representative of all involved organs, should be identified as target lesions and recorded and measured at baseline. Target lesions should be selected on the basis of their size (lesions with the longest diameter), be representative of all involved organs, but in addition should be those that lend themselves to reproducible repeated measurements. It may be the case that, on occasion, the largest lesion does not lend itself to reproducible measurement in which circumstance the next largest lesion that can be measured reproducibly should be selected. A sum of the diameters (longest for non-nodal lesions, short axis for nodal lesions) for all target lesions will be calculated and reported as the baseline sum diameters. If lymph nodes are to be included in the sum, then only the short axis is added into the sum. The baseline sum diameters will be used as reference to further characterize any objective tumor regression in the

measurable dimension of the disease. Target lesions will not include radiated tumor sites for this study unless all tumor sites have been radiated.

12.4. Non-target Lesions

All other lesions (or sites of disease) including any measurable lesions over and above the 5 target lesions should be identified as non-target lesions and should also be recorded at baseline. Measurements of these lesions are not required, but the presence, absence, or in rare cases unequivocal progression of each should be noted throughout follow-up.

12.5. Evaluation of Target Lesions

NOTE: In addition to the information below, also see section 4.3.2 in the international criteria proposed by the Response Evaluation Criteria in Solid Tumors (RECIST) Committee, version 1.1 (Eur J Cancer 45;2009:228-247) for special notes on the assessment of target lesions.

Complete Response (CR)	Disappearance of all target lesions. Any pathological lymph nodes (whether target or non-target) must have reduction in short axis to <10 mm.
Partial Response (PR)	At least a 30 % decrease in the sum of the diameters of target lesions, taking as reference the baseline sum diameters
Progressive Disease (PD)	At least a 20 % increase in the sum of the diameters of target lesions, taking as reference the smallest sum on study (this includes the baseline sum if that is the smallest on study). In addition to the relative increase of 20 %, the sum must also demonstrate an absolute increase of at least 5 mm. (Note: the appearance of one or more new lesions is also considered progressions).
Stable Disease (SD)	Neither sufficient shrinkage to qualify for PR nor sufficient increase to qualify for PD, taking as reference the smallest sum diameters while on study

12.6. Evaluation of Non-target Lesions

Complete Response (CR)	Disappearance of all non-target lesions and normalization of tumor marker level. All lymph nodes must be non-pathological in size (< 10 mm short axis) Note: If tumor markers are initially above the upper normal limit, they must normalize for a subject to be considered in complete clinical response.
Non-CR/ Non-PD	Persistence of one or more non-target lesion(s) and/or maintenance of tumor marker level above the normal limits
Progressive Disease (PD)	Appearance of one or more new lesions and/or unequivocal progression of existing non-target lesions. Unequivocal

	progression should not normally trump target lesion status. It must be representative of overall disease status change, not a single lesion increase.
--	-------------------------------------------------------------------------------------------------------------------------------------------------------

Although a clear progression of “non-target” lesions only is exceptional, the opinion of the site investigator should prevail in such circumstances, and the progression status should be confirmed at a later time by the sponsor investigator.

12.7. Evaluation of Best Overall Response

Target Lesions	Non-Target Lesions	New Lesions	Overall Response
CR	CR	No	CR
CR	Non-CR/ Non-PD	No	PR
CR	Not evaluated	No	PR
PR	Non-PD/ or not all evaluated	No	PR
SD	Non-PD or not all evaluated	No	SD
Not all evaluated	Non-PD	No	Non-evaluable
PD	Any	Yes or No	PD
Any	PD*	Yes or No	PD
Any	Any	Yes	PD

*In exceptional circumstances, unequivocal progression in non-target lesions may be accepted as disease progression.

Subjects with a global deterioration of health status requiring discontinuation of treatment without objective evidence of disease progression at that time should be classified as having “symptomatic deterioration”. Every effort should be made to document the objective progression even after discontinuation of treatment.

In some circumstances it may be difficult to distinguish residual disease from normal tissue. When the evaluation of complete response depends on this determination, it is recommended that the residual lesion be investigated (fine needle aspirate/biopsy) to confirm the complete response status.

